**Table 9.a Criteria for Dose Adjustments and Delays**

Toxicity	Grade 1	Grade 2	Grade 3	Grade 4
Non-hematologic	Continue at the same dose level (1.8 mg/kg).	Continue at the same dose level (1.8 mg/kg), except in the event of Grade 2 neuropathy. For Grade 2 neuropathy, withhold dose until toxicity is $\leq$ Grade 1 or has returned to baseline, then resume treatment at the same dose level (1.8 mg/kg). For the second occurrence of Grade 2 neuropathy, withhold dose until toxicity is $\leq$ Grade 1, then reduce the dose to 1.2 mg/kg and resume treatment after discussion with the sponsor.	The investigator/subinvestigator will make decisions on the appropriateness of brentuximab vedotin treatment in subsequent cycles after discussion with the sponsor. For subjects who are determined to be able to continue treatment with brentuximab vedotin, continue treatment at the same dose level (1.8 mg/kg) or by reducing the dose to 1.2 mg/kg. Confirm that toxicity is $\leq$ Grade 1 or has returned to baseline before continuing treatment (a). For Grade 3 or higher neuropathy, consider discontinuing treatment after discussion with the sponsor.	The investigator/subinvestigator will make decisions on the appropriateness of brentuximab vedotin treatment in subsequent cycles after discussion with the sponsor. For subjects who are determined to be able to continue treatment with brentuximab vedotin, confirm that toxicity is $\leq$ Grade 1 or has returned to baseline, then continue treatment by reducing the dose to 1.2 mg/kg (a).
Hematologic	Continue at the same dose level (1.8 mg/kg).		The investigator/subinvestigator will make decisions on the appropriateness of brentuximab vedotin treatment in subsequent cycles after discussion with the sponsor. For subjects who are determined to be able to continue treatment with brentuximab vedotin, continue treatment at the same dose level (1.8 mg/kg) or by reducing the dose to 1.2 mg/kg. Confirm that toxicity is $\leq$ Grade 2 or has returned to baseline before continuing treatment (b). Consider growth factor support (G-CSF or GM-CSF) for treatment of neutropenia and prophylaxis in subsequent cycles.	The investigator/subinvestigator will make decisions on the appropriateness of brentuximab vedotin treatment in subsequent cycles after discussion with the sponsor. For subjects who are determined to be able to continue treatment with brentuximab vedotin, continue treatment at the same dose level (1.8 mg/kg) or by reducing the dose to 1.2 mg/kg. Confirm that toxicity is $\leq$ Grade 2 before continuing treatment (b). Consider growth factor support (G-CSF or GM-CSF) for treatment of neutropenia and prophylaxis in subsequent cycles. For the second occurrence of Grade 4 toxicity (if neutropenia, while receiving growth factor support), the investigator/subinvestigator will make decisions on the appropriateness of brentuximab vedotin treatment in subsequent cycles after discussion with the sponsor. For subjects who are determined to be able to continue treatment with brentuximab vedotin, confirm that toxicity is $\leq$ Grade 2, then continue treatment by reducing the dose to 1.2 mg/kg (b).

G-CSF= granulocyte colony-stimulating factor, GM-CSF= granulocyte macrophage colony-stimulating factor.

(a) Patients who develop Grade 3 or 4 electrolyte laboratory abnormalities may continue study treatment without dose delay.

(b) Patients who develop Grade 3 or 4 lymphopenia may continue study treatment without dose delay.

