#### **4.1.5 Known or Potential Risks of Brentuximab Vedotin**

- Brentuximab vedotin treatment causes peripheral neuropathy, both sensory and motor. Brentuximab vedotin-induced peripheral neuropathy is typically cumulative and generally reversible. Monitoring patients for symptoms of neuropathy, such as hypoesthesia, hyperesthesia, paresthesia, discomfort, a burning sensation, and neuropathic pain or weakness, is required. Patients experiencing new or worsening peripheral neuropathy may require brentuximab vedotin dose modifications, including a dose delay (see [Table 9.a](#)).
- Complete blood counts should be monitored before each dose of brentuximab vedotin, and more frequent monitoring should be considered for patients with Grade 3 or 4 neutropenia. Prolonged ( $\geq 1$  week) severe neutropenia can occur. If Grade 3 or 4 neutropenia develops, manage with dose delays, reductions, or discontinuations (see [Table 9.a](#)).
- Infusion-related reactions, including anaphylaxis, have occurred with brentuximab vedotin. Monitoring of patients during infusion is required. If anaphylaxis occurs, the administration of brentuximab vedotin should be immediately and permanently discontinued and appropriate medical therapy administered. Patients who have experienced a prior infusion-related reaction should be premedicated according to institutional guidelines for subsequent infusions. Premedication may include acetaminophen, an antihistamine, and a corticosteroid.

- Any treatment that can decrease immune function may contribute to malignancy and infections; patients are to be monitored for these events during the treatment period and up to and including 30 days after the last dose.
- Stevens-Johnson syndrome (SJS)/toxic epidermal necrolysis (TEN) have been reported with brentuximab vedotin. If SJS/TEN occurs, brentuximab vedotin must be discontinued and the appropriate medical therapy administered.
- Tumor lysis syndrome may occur. Patients with rapidly proliferating tumors and high tumor burden are at risk of tumor lysis syndrome and should be closely monitored. If tumor lysis syndrome occurs, take medically appropriate measures.
- Progressive multifocal leukoencephalopathy (PML) has been reported with brentuximab vedotin use. If PML is suspected, a diagnostic work-up should be performed as described in Section 9.6.5.

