### **9.2 Dose Modification Guidelines**

If treatment-related toxicity occurs, intrapatient dose reduction will be allowed to 1.2 mg/kg for each subject depending on the type and severity of the toxicity. If a patient requires further dose reductions, brentuximab vedotin will be permanently discontinued. Table 9.a provides the criteria for dose adjustments and delays for treatment-related toxicity. Toxicity will be evaluated according to the NCI CTCAE, version 4.03 [2].

If a patient fails to meet the criteria for re-treatment cited in Table 9.a, initiation of the next cycle of treatment should be delayed up to 1 week. At the end of that time, the patient should be re-evaluated to determine whether the criteria for re-treatment have been met. The start of the next cycle may be delayed for up to 3 weeks (6 weeks after the most recent dose) if additional time is

required for the patient to recover from treatment-related toxicity experienced during the current cycle. Delays of longer than 3 weeks (after Day 22) are prohibited without approval from the sponsor.

Doses reduced for treatment-related toxicity should generally not be re-escalated; however, intrapatient re-escalation to 1.8 mg/kg may be permitted at the discretion of the investigator after a discussion with the sponsor.

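### In Table 9.a, a Grade 3 neuropathy may resume at 1.8 or 1.2 mg/kg, while a milder second Grade 2 neuropathy must resume at 1.2 mg/kg

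*Protocol*

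**What the plan says.** Protocol Table 9.a has one row for all non-hematologic toxicity, with neuropathy exceptions inside some cells.

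- **First Grade 2 neuropathy:** hold until Grade 1 or lower, or baseline, then resume at 1.8 mg/kg.
- **Second Grade 2 neuropathy:** hold until Grade 1 or lower, "then reduce the dose to 1.2 mg/kg and resume treatment after discussion with the sponsor". No other dose is offered.
- **Grade 3, any non-hematologic toxicity:** the investigator decides after sponsor discussion whether the patient can go on. If so, "continue treatment at the same dose level (1.8 mg/kg) or by reducing the dose to 1.2 mg/kg", once recovery to Grade 1 or lower, or baseline, is confirmed. For neuropathy the cell adds: "For Grade 3 or higher neuropathy, consider discontinuing treatment after discussion with the sponsor".
- **Grade 4, any non-hematologic toxicity:** the same individual decision, but 1.2 mg/kg is the only dose listed for continuing.

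Section 9.2 adds two general rules. A patient who needs a further reduction below 1.2 mg/kg stops permanently. On going back up, "Doses reduced for treatment-related toxicity should generally not be re-escalated", although "intrapatient re-escalation to 1.8 mg/kg may be permitted at the discretion of the investigator after a discussion with the sponsor".

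Section 9.6.4 sends neuropathy above Grade 1 back to Table 9.a and sets no dose of its own. Section 4.1.5 also refers to Table 9.a and describes the toxicity: "Brentuximab vedotin-induced peripheral neuropathy is typically cumulative and generally reversible".

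**The concern.** One expects the dose after recovery to stay level or fall as the preceding event gets worse. Here the neuropathy rule tightens at a second Grade 2 event, loosens at Grade 3, and tightens again at Grade 4.

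At Grade 2 the table takes neuropathy out of the general rule and handles it more cautiously than other non-hematologic toxicity. At Grade 3 the neuropathy sentence deals only with stopping, so the dose falls back on the general rule. The documents do not show whether this was intended.

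What is at stake is the first dose given after recovery from a toxicity that the protocol regards as cumulative. After a second Grade 2 event the dose comes down first, and any return to 1.8 mg/kg is a separate step against a general presumption. After Grade 3, 1.8 mg/kg can be the first dose given. With approximately 7 sites (Section 2.0) and no data safety monitoring committee (Section 12.0), uniform handling depends on individual discussions with the sponsor.

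**Working it through.** The plan gives no figure to reproduce. The check is a comparison of the cells, followed by simple arithmetic on size.

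**Step 1: the rules side by side for neuropathy.**

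| Event | Whether to continue | Recovery needed | Dose on resuming |
|---|---|---|---|
| First Grade 2 | Yes, after a hold | Grade 1 or lower, or baseline | 1.8 mg/kg |
| Second Grade 2 | Yes, after a hold and sponsor discussion | Grade 1 or lower | 1.2 mg/kg |
| Grade 3 | Individual decision after sponsor discussion; consider stopping | Grade 1 or lower, or baseline | 1.8 or 1.2 mg/kg |
| Grade 4 | Same, as the advice to consider stopping covers Grade 3 or higher | Grade 1 or lower, or baseline | 1.2 mg/kg |

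The highest permitted resumption dose runs 1.8, 1.2, 1.8, 1.2 mg/kg down the table. It is not ordered by severity.

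**Step 2: does the recovery threshold make up for it?** No. Exclusion criterion 6 (Section 8.2) keeps out patients with neuropathy of Grade 2 or higher, so a return to baseline also means Grade 1 or lower. Both paths need the same recovery.

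**Step 3: does another section close the gap?** No. Section 9.6.4 requires a dose modification above Grade 1, but Section 4.1.5 counts a delay as a modification, so a hold followed by 1.8 mg/kg complies. Section 9.2 sets no dose for Grade 3 neuropathy. Its limit on delay (up to 3 weeks, longer only with sponsor approval) applies to both paths.

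**Step 4: one patient, two outcomes.** Take a patient at 1.8 mg/kg with one earlier Grade 2 neuropathy. If the next event is Grade 2, it is the second occurrence and the dose is 1.2 mg/kg. If it is Grade 3, it falls in the Grade 3 column, where 1.8 mg/kg is a listed option. The table does not address this sequence explicitly; this is its literal reading.

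**Step 5: size per patient.** The difference per infusion is 1.8 − 1.2 = 0.6 mg/kg. As an illustration, assume resumption between Cycle 9 and Cycle 16 and no later dose change on either path.

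- Resuming at Cycle 9 leaves 16 − 9 + 1 = 8 doses: 8 × 1.8 = 14.4 against 8 × 1.2 = 9.6 mg/kg, a difference of 4.8 mg/kg.
- Resuming at Cycle 16 leaves 1 dose: a difference of 0.6 mg/kg.

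**Step 6: how many patients.** Section 4.1.4 reports peripheral sensory neuropathy of any grade in 44% of phase 2 patients, and describes the common events as mainly mild to moderate. For about 30 patients (Section 7.2), 0.44 × 30 = 13.2. The documents give no Grade 3 rate. If it is assumed to be 2% to 10%, then 0.02 × 30 = 0.6 and 0.10 × 30 = 3.0 patients. Under that assumption this is an upper bound, because a patient is affected only if still on 1.8 mg/kg, recovered, judged able to continue, and kept at 1.8 mg/kg.

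**The case against.** The strongest objection is that recurrence and severity are different triggers. A second Grade 2 event has come back after re-treatment at 1.8 mg/kg, which for a cumulative toxicity is a sound reason to reduce. Compared as first events, the row does rise with severity: 1.8 mg/kg at Grade 2, a choice at Grade 3, 1.2 mg/kg at Grade 4. The choice of two doses is also an established pattern, since the hematologic row uses it at Grade 3 and at a first Grade 4 event. That row has no inversion, but its recurrence rule sits in the highest grade column, where none could arise, so the contrast proves little.

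This explains how the rule may have come about. It does not answer the patient in Step 4, who has the same history on both branches and gets the looser dose rule after the worse event.

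Three further points stand and limit the finding. Grade 3 is stricter on whether to continue. The 1.2 mg/kg dose after a second Grade 2 event is a starting dose, because Section 9.2 leaves a route back to 1.8 mg/kg. And sponsor discussion is required on both paths, although for a second Grade 2 event the table fixes the dose as well.

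A reader might infer that the protocol treats Grade 3 neuropathy more leniently overall, or that it directs resumption at 1.8 mg/kg. Neither follows. The cell prompts consideration of stopping, and it lists two doses without preferring one.

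**Conclusion.** The inconsistency is real and minor. On resumption dose alone, Grade 3 neuropathy has a looser rule than a second Grade 2 event, by up to 0.6 mg/kg per infusion. This rests on reading the table literally for a Grade 3 event that follows an earlier Grade 2 event.

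The number of patients is probably small, and the 0.6 to 3 of 30 rests on an assumed rate. The mg/kg totals are differences in exposure; no harm has been estimated.

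A reader might also infer damage to the primary analysis. The documents do not support that. The ORR analysis is unaffected. Adverse events are also a primary endpoint (Section 6.1), and SAP Section 7.11.1.2 summarizes the onset, resolution and improvement of neuropathy, so it would be wrong to say that no primary endpoint is touched. But no material effect on the analysis of adverse events is shown. This is a point about dosing consistency and patient safety, worth fixing because the fix is cheap.

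**What to change.** Add to the non-hematologic Grade 3 cell of Table 9.a:

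*For Grade 3 neuropathy in a patient receiving 1.8 mg/kg, if treatment is not discontinued, resume at 1.2 mg/kg after recovery to Grade 1 or lower, or baseline. For a patient already at 1.2 mg/kg, Section 9.2 applies (permanent discontinuation if a further reduction is required).*

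The second sentence matters. Without it, the addition could be read as allowing a patient who reaches Grade 3 on 1.2 mg/kg to be re-treated at that same dose, against the Section 9.2 rule. With the change, the resumption doses run 1.8, 1.2, 1.2, 1.2 mg/kg for a patient on 1.8 mg/kg, and no worse event has a looser dose rule than a milder one.

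The cost is two sentences in a protocol amendment and a site memo, with no added procedures. The downside is less initial discretion to keep 1.8 mg/kg after Grade 3 neuropathy. The re-escalation route in Section 9.2 remains, so the full dose can still be reached by a separate, deliberate step.

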### **9.3 Excluded Concomitant Medications and Procedures**

The following medications and procedures are prohibited from enrollment to completion of the safety follow-up assessments:

- Antineoplastic agents other than brentuximab vedotin.
- Any surgery requiring general anesthesia.
- Radiotherapy.
- Any other investigational drugs.
- Any other investigational device.
- Long-term treatment with corticosteroids at doses greater than the equivalent of 20 mg/day of prednisone.

### **9.4 Permitted Concomitant Medications and Procedures**

- Patients are allowed to receive treatment with corticosteroids at doses less than or equal to the equivalent of 20 mg/day of prednisone for longer than 1 month before enrollment. Intermittent use of corticosteroids for treating hypersensitivity reactions is permitted.
- The use of platelet and/or red blood cell supportive growth factors or transfusions when applicable is allowed.
- The use of colony-stimulating factors for the treatment of neutropenia per institutional practice is permitted during therapy.

Co-administration of brentuximab vedotin with ketoconazole, a strong CYP3A4 and P-gp inhibitor, increased the exposure to the antimicrotubule agent MMAE by approximately 73% and did not alter the plasma exposure to brentuximab vedotin. Therefore, co-administration of brentuximab vedotin with strong CYP3A4 and P-gp inhibitors may increase the incidence of neutropenia. If neutropenia develops, refer to [Table 9.a](#).

Co-administration of brentuximab vedotin with rifampicin, a strong CYP3A4 inducer, did not alter the plasma exposure to brentuximab vedotin; however, it reduced exposure to MMAE by approximately 31%.

Co-administration of midazolam, a CYP3A4 substrate, with brentuximab vedotin did not alter the metabolism of midazolam; therefore, brentuximab vedotin is not expected to alter the exposure to medicines that are metabolized by CYP3A4 enzymes.

### **9.5 Precautions and Restrictions**

It is not known what effects brentuximab vedotin has on human pregnancy or development of the embryo or fetus; therefore, female patients participating in this study should avoid becoming pregnant, and male patients should avoid impregnating a female partner. Nonsterilized female

patients of reproductive age and male patients should use effective methods of contraception through defined periods during and after study treatment as specified below.

Female patients must meet 1 of the following:

- Postmenopausal for at least 1 year before the screening visit, OR
- Surgically sterile, OR
- If they are of childbearing potential, agree to practice 2 effective methods of contraception from the time of signing of the informed consent form (ICF) through 6 months after the last dose of brentuximab vedotin.

Male patients, even if surgically sterilized (ie, status postvasectomy) must agree to 1 of the following:

- Practice effective barrier contraception during the entire study treatment period and through 6 months after the last dose of brentuximab vedotin.

Contraception methods meeting the criteria defined above are provided below. If male condoms are used as a barrier method by male subjects, his partner must use an intrauterine devices (Copper T, or Progesteron T) or hormonal contraceptive (combined pills) instead of spermicide.

Barrier Methods (Each Time the Subject Has Intercourse)	Intrauterine Devices	Hormonal Contraceptives

• Male condom PLUS spermicide.

• Cap (plus spermicidal cream or jelly) PLUS male condom and spermicide.

• Diaphragm (plus spermicidal cream or jelly) PLUS male condom and spermicide.

	

• Copper T PLUS condom or spermicide.

• Progesterone T PLUS condom or spermicide.

	

• Implants.

• Hormone injections.

• Combined pills.

• Minipills.

• Patches.

• Vaginal ring PLUS male condom and spermicide.

## **9.6 Management of Clinical Events**

### **9.6.1 Nausea and/or Vomiting**

Although this study will not require prophylactic antiemetics, there is no prohibition against their use.

### **9.6.2 Diarrhea**

Prophylactic antidiarrheals will not be used in this protocol; however, patients will be instructed to take antidiarrheal medication(s) at their physician's discretion until they are diarrhea-free for at least 12 hours. Fluid intake should be maintained to avoid dehydration.

### **9.6.3 Infusion-Related Reactions**

Infusion-related reactions may occur during the infusion of brentuximab vedotin. The infusion should be administered at a site properly equipped and staffed to manage an infusion-related reaction, including anaphylaxis should it occur. The patient should be observed for approximately 60 minutes following the first infusion of brentuximab vedotin. During this observation period, the IV line should remain open for at least 1 hour to allow administration of IV drugs if necessary. All supportive measures consistent with optimal patient care will be given throughout the study according to institution standards. Medications for infusion-related reactions, such as epinephrine and antihistamines, should be available for immediate use.

Patients who experience a Grade 1 or 2 infusion-related reaction may receive subsequent brentuximab vedotin infusions with premedication consisting of acetaminophen (650 mg orally) and diphenhydramine (25-50 mg orally or 10-25 mg IV) or according to institutional standards, administered 30 to 60 minutes before each 30-minute brentuximab vedotin infusion.

### **9.6.4 Peripheral Neuropathy**

AEs of peripheral neuropathy will be monitored closely throughout the study. These events may include, but are not limited to, peripheral sensory neuropathy, peripheral motor neuropathy, paresthesia, hypoesthesia, polyneuropathy, muscular weakness, and demyelinating polyneuropathy. Such events, regardless of seriousness, will be followed for all changes in severity until the sooner of resolution to baseline or study closure and recorded in the electronic case report form (eCRF). Events that are higher than Grade 1 will result in brentuximab vedotin dose modification as shown in [Table 9.a](#).

### **9.6.5 Suspected PML**

Signs and symptoms of PML may include altered mental status, motor deficits such as hemiparesis or ataxia, visual disturbances, or higher cortical dysfunction such as dysphasia or agnosia. See the IB for further details.

If PML is suspected, hold further dosing and undertake a diagnostic work-up including (but not limited to):

- Neurologic examinations, as warranted.
- Brain magnetic resonance imaging (MRI): Features suggestive of PML include the presence of unifocal or multifocal lesions, mainly of the white matter, which are typically nonenhancing and do not have mass effect.
- Polymerase chain reaction analysis: John Cunningham virus (JCV) DNA detectable in cerebrospinal fluid or evidence of JCV in a brain biopsy.
- Neurology consultation.

If PML is confirmed, permanently discontinue treatment with brentuximab vedotin.

## **9.7 Blinding and Unblinding**

This is an open-label study.

## **9.8 Description of Investigational Agents**

Brentuximab vedotin is manufactured by BSP Pharmaceuticals S.p.A (formerly named BSP Pharmaceuticals S.r.l.) (Italy) under the manufacturing license issued by Takeda Pharma A/S (Denmark).

Brentuximab vedotin is a sterile, preservative-free, white to off-white lyophilized cake or powder supplied in single-use vials. Each vial contains brentuximab vedotin, trehalose, sodium citrate, and polysorbate 80.

For further details, see the IB.

## **9.9 Preparation, Reconstitution, and Dispensation**

Brentuximab vedotin is supplied in single-use glass vials and will be reconstituted in the vial with 10.5 mL of sterile water for injection. The appropriate amount of reconstituted brentuximab vedotin should be withdrawn from the vial and diluted in an infusion bag containing saline solution to produce a final brentuximab vedotin concentration of 0.4 to 1.8 mg/mL. For further details, see the Pharmacy Manual.

Parenteral drug products should be inspected visually for particulate matter and discoloration before administration whenever the solution and container permit.

Brentuximab vedotin is an anticancer drug, and as with other potentially toxic compounds, caution should be exercised when handling brentuximab vedotin.

